### Summary of Significant Changes to the Protocol

Section	Change
Throughout Document	Minor edits for grammar, spelling, and typos.
Throughout Document: General Explanation	
Primary Reasons for Amendment:
 
Inclusion criterion 4 stated that “at least 2, but no more than 4, prior HER2-directed therapy regimens for breast cancer, including trastuzumab and trastuzumab emtansine (T-DM1, KADCYLA®)”. The majority of patients with advanced HER2 positive breast cancer have been treated with more than 4 regimens of prior anti-cancer therapies. The restriction of patients having only up to 4 prior treatment regimens significantly limits a patient’s participation opportunity. In order to include more patients, the inclusion criterion was changed so that a patient must have had at least 2 prior treatments, but there is no upper limit.
 
A change to the prior treatment washout requirement was based on the half-life of the treatments and to ensure provide enough time for recovery from side effects and minimization of influences from prior therapy. This change is intended to provide patients with study treatment earlier, as appropriate.
 
Other changes in patient eligibility are based on the feedback from the investigators and study centers. These changes are expected to improve enrollment without an increased risk to patient safety.

Throughout Document:	
Original Text: at least 2, but no more than 4, prior HER2-directed therapy regimens...
 
New Text: at least 2, <del>but no more than 4</del>, prior HER2-directed therapy regimens
 
Reason: To allow more patients to participate in the trial

Title Page Footer Synopsis	
Original Text: Protocol Version/Date: <del>Amendment 1/17 Feb 2017</del>
 
New Text: Protocol Version/Date: Amendment 2/14 Jul 2017

Synopsis: Inclusion and Exclusion Criteria Section 4	
Original Text:
 
Inclusion Criteria:
 
 
At least 2, <del>and no more than 4</del>, prior HER2-directed therapy regimens for breast cancer, including trastuzumab and trastuzumab emtansine (T-DM1, KADCYLA®).
 

Section	Change
	
2. Patient has adequate hematologic, hepatic, and renal function, as defined by:
 
 
• Absolute neutrophil count (ANC) <math>\geq 1.5 \times 10^9/L</math>
 
 
3. Patient has an Eastern Cooperative Oncology Group (ECOG) performance status <math>\leq 2</math>.
 
Exclusion Criteria:
 
4. Patient has brain metastases that are symptomatic or require therapy to control symptoms, as well as any history of radiation, surgery, or other therapy, including steroids, to control symptoms from brain metastases within 1 month (30 days) of enrollment.
 
5. Patient has received anticancer chemotherapy, biologics, immunotherapy, cure-intent radiotherapy, or investigational treatment within 30 days, except for hormone therapy, palliative therapy, or supportive therapy
 
New Text:
 
Inclusion Criteria:
 
4. At least 2 prior HER2-directed therapy regimens for breast cancer, including trastuzumab and trastuzumab emtansine (T-DM1, KADCYLA®).
 
6. Patient has adequate hematologic, hepatic, and renal function, as defined by:
 
 
• Absolute neutrophil count (ANC) <math>\geq 1.0 \times 10^9/L</math>
 
 
7. Patient has an Eastern Cooperative Oncology Group (ECOG) performance status <math>\leq 2</math>. Life expectancy is more than 6 months.
 
Exclusion Criteria:
 
2. Patient has brain metastases that are symptomatic or require therapy to control symptoms, as well as any history of radiation, surgery, or other therapy, including steroids, to control symptoms from brain metastases within 15 days of enrollment.
 
3. Patient has received anticancer chemotherapy, biologics, immunotherapy, cure-intent radiotherapy, or investigational treatment within 15 days, except for hormone therapy, palliative therapy, or supportive therapy
 
Reasons:
 
Inclusion:
 
4. Reason discussed above.
 
6. Investigators believe that <math>ANC \geq 1.0 \times 10^9/L</math> is acceptable for enrollment and patient safety will not be at risk.
 
7. In order to measure the response properly, and since the limit of prior treatments has been removed, we have stipulated that patients must have a life expectancy of at least 6 months.
 
Exclusion:
 
2 and 3. Based on the half-life of the drugs, a 15-day washout was deemed adequate for enrollment into the study.


Section	Change

Synopsis: Pharmacokinetic Assessments Schedule of Assessments and Procedures Section 5.3.2 Section 5.4.6
	
Original Text: The schedule for intensive PK sampling will be Day 1 of Cycle 1 pre-dose and 30 minutes, 1, 1.5, 2, 3, 4, <del>8, 12</del>, and 24 hours post-dose.
 
New Text: The schedule for intensive PK sampling will be Day 1 of Cycle 1 pre-dose and 30 minutes, 1, 1.5, 2, 3, 4, 6, and 24 hours post-dose.
 
Reason: The change was made to improve enrollment.

Section 5.4.5: Chemistry Panel
	
Added: Added GGT (only at screening) and uric acid as part of the chemistry panel.
 
Reason: These were already part of the chemistry panel but are now specified.

## SYNOPSIS

Title of Study: A Phase 2 Study of Poziotinib in Patients with HER2-Positive Metastatic Breast Cancer (MBC) Who Have Received Prior HER2 Regimens for MBC	
Name of Sponsor: Spectrum Pharmaceuticals, Inc.	
Name of Investigational Product: Poziotinib	
Study Centers: Approximately 35 study centers	
Planned Number of Patients: Approximately 75 patients	
Duration of Study: Approximately 3 years	Clinical Phase: 2

Objectives:
 
Primary Objective
 
 
To establish the dosing schedule for poziotinib to be used in the clinical development program
 
To evaluate the Objective Response Rate (ORR) of poziotinib in patients with human epidermal growth factor receptor 2 (HER2)-positive metastatic breast cancer (MBC)
 
 
Secondary Objectives
 
 
To assess the safety and tolerability of poziotinib in patients with HER2-positive MBC
 
To evaluate the pharmacokinetics of poziotinib in patients with HER2-positive MBC
 
To evaluate other efficacy variables of poziotinib in patients with HER2-positive MBC, including the following:           
 
Progression Free Survival (PFS)
 
Disease Control Rate (DCR)
 
Time to Progression (TTP)
 
 
 
	

Duration of Study: The total duration of the study will be approximately 3 years. The duration of study participation for each patient includes the following segments:
 
 
Screening Period: 30 days
 
Treatment Period: 21 days per cycle for up to 24 months
 
End-of-Treatment Visit: 35 (<math>\pm</math>5) days after the last dose of poziotinib
 
	

Study Design and Treatment Plan:
 
This is a Phase 2, open-label, multicenter study to establish the dose regimen and evaluate the preliminary efficacy and the safety/tolerability of poziotinib in approximately 75 patients with HER2-positive MBC who have received at least two prior HER2-directed treatment regimens including trastuzumab and T-DM1. The Screening period (Day -30 to Day -1) lasts up to approximately 30 days prior to Cycle 1, Day 1. Patients must meet all Inclusion/Exclusion Criteria to participate in the study. Eligible patients will provide written Informed Consent prior to undergoing any study procedures.
 
Each treatment cycle is 21 calendar days in duration. Eligible patients will be enrolled into each dose cohort as described below. In Amendment 1, in addition to the original 24 mg cohort (Cohort 1), two additional treatment cohorts are being added:
 
 
Cohort 1: 24 mg (three 8-mg tablets once daily) for 2 weeks, rest 1 week (ENROLLMENT COMPLETE)
 
Cohort 2: 16 mg (two 8-mg tablets once daily) continuous dosing
 
Cohort 3: 12 mg (one 8-mg tablet and two 2-mg tablet once daily) continuous dosing
 
 
Patient enrollment in Cohort 1 is complete. New patients will begin enrollment into Cohort 2. Rules for safety review and enrollment for Cohort 2 and Cohort 3 follow:
	

**Cohort 2:**

- Rate of Grade 3 or greater AEs of special interest (ie, diarrhea, skin rash, stomatitis) that are identified during Safety Data Review after the first 6 patients and again after 12 patients have completed **Cycle 1**:
  - **>33%: Stop Cohort 2** ( $\geq 3$  of 6 patients or  $\geq 5$  of 12 patients with Grade 3 or greater AEs of special interest) and begin **Cohort 3**
  - **$\leq 33\%$ : Keep enrolling Cohort 2** until 30 patients are enrolled and treated and no additional patients will be enrolled.

**Cohort 3 - only if Cohort 2 is stopped due to toxicity:**

- Rate of Grade 3 or greater AEs of special interest (ie, diarrhea, skin rash, stomatitis) are identified during Safety Data Review after the first 6 patients and again after 12 patients have completed **Cycle 1**:
  - **>33%: End enrollment in Cohort 3**
  - **$\leq 33\%$ : Keep enrolling Cohort 3** until 20 patients are enrolled and treated

Toxicity will be assessed based on the grade of the Adverse events using CTCAE version 4.03.

All treatments will be taken orally, once daily (QD) at approximately the same time each morning. On **Day 1** of each cycle, the patient's absolute neutrophil count (ANC) must be  $\geq 1.0 \times 10^9/L$  and platelet count must be  $\geq 100 \times 10^9/L$  before administering poziotinib. **Day 1** of a new cycle is equivalent to **Day 22** of the previous cycle, with a window of  $\pm 3$  days for the visit. If a visit is delayed during a cycle, then all subsequent cycles will be delayed sequentially. All patients will be treated until disease progression, death, intolerable adverse events, or up to a maximum of 24 months, whichever comes first.

**Patient Replacement Strategy:** Patients who discontinue from the study will not be replaced.

**Inclusion & Exclusion Criteria:**

**Inclusion Criteria:**

1. Patient, or patient's authorized representative, must be willing and capable of giving written Informed Consent and must be able to adhere to dosing and visit schedules as well as meet all study requirements.
2. Patient has histopathologically confirmed primary breast cancer with metastatic lesions.
3. Patient has confirmed HER2 overexpression or gene-amplified tumor via immunohistochemistry (IHC) with IHC 3+ or IHC 2+ with confirmatory fluorescence *in situ* hybridization (FISH)+.
4. At least two prior HER2-directed therapy regimens for breast cancer, including trastuzumab and trastuzumab emtansine (T-DM1, KADCYLA®).
5. Patient is at least 18, and  $\leq 90$  years of age.
6. Patient has adequate hematologic, hepatic, and renal function, as defined by:
  - Absolute neutrophil count (ANC)  $\geq 1.0 \times 10^9/L$ .
  - Platelet count  $\geq 100 \times 10^9/L$
  - Hemoglobin  $\geq 9$  g/dL
  - Total bilirubin  $\leq 1.5$  mg/dL, if hepatic metastases are present,  $\leq 2.5$  mg/dL
  - Aspartate aminotransferase/serum glutamic-oxaloacetic transaminase (AST/SGOT), alanine aminotransferase/serum glutamic-pyruvic transaminase (ALT/SGPT), and gamma-glutamyltransferase (GGT)  $\leq 2.5 \times$  upper limit of normal (ULN); if hepatic metastases are present,  $\leq 5.0 \times ULN$
  - Creatinine  $\leq 2.2$  mg/dL or calculated creatinine clearance  $\geq 40$  mL/min
7. Patient has an Eastern Cooperative Oncology Group (ECOG) performance status  $\leq 2$ . Life expectancy is more than 6 months.
8. Patient has measurable disease, as per the Response Evaluation Criteria in Solid Tumors (RECIST, version 1.1)
9. Patient is willing to practice 2 forms of contraception, one of which must be a barrier method, from study entry until at least 30 days after the last dose of poziotinib.

10. Females of childbearing potential must have a negative pregnancy test within 30 days prior to enrollment. Females who are postmenopausal for at least 1 year (defined as more than 12 months since last menses) or who are surgically sterilized do not require this test.

**Exclusion Criteria:**

1. Patient has had previous treatment with poziotinib prior to study participation.
2. Patient has brain metastases that are symptomatic or require therapy to control symptoms, as well as any history of radiation, surgery, or other therapy, including steroids, to control symptoms from brain metastases within 15 days of enrollment.
3. Patient has received anticancer chemotherapy, biologics, immunotherapy, cure-intent radiotherapy, or investigational treatment within 15 days, except for hormone therapy, palliative therapy, or supportive therapy
4. Patient has a history of congestive heart failure (CHF) Class III/IV according to the New York Heart Association (NYHA) Functional Classification or serious cardiac arrhythmias requiring treatment.
5. Patient has a cardiac ejection fraction <50% by either echocardiogram or multi-gated acquisition (MUGA) scan.
6. Patient has a history of other malignancies within the last 5 years, except for non-melanoma skin cancer or carcinoma *in situ* of the cervix.
7. Patient is confirmed to have clinically significant or recent acute gastrointestinal disease presenting as diarrhea and/or colenteritis as a main symptom (ie, acute enteritis, malabsorption, or Common Terminology Criteria for Adverse Events (CTCAE, version 4.03) Grade 2 or above diarrhea due to other etiologies).
8. Patient is unable to take drugs orally due to disorders or diseases that may affect gastrointestinal function, such as inflammatory bowel diseases (eg, Crohn's disease, ulcerative colitis) or malabsorption syndrome, or procedures that may affect gastrointestinal function, such as gastrectomy, enterectomy, or colectomy.
9. Patient has an active liver disease or biliary tract disease (except for Gilbert's disease, asymptomatic biliary stones, liver metastasis, or stabilized chronic liver diseases).
10. Patient has an active uncontrolled infection, underlying medical condition, or other serious illness that would impair the ability of the patient to receive protocol treatment.
11. Patient has active bleeding disorders, uses warfarin or other coumadin-derived anticoagulants, has abnormal International Normalized Ratio (INR), or abnormal prothrombin time test within one month prior to the study.
12. Patient is pregnant or breast-feeding.

**Investigational Product, Dose, and Route of Administration:**

Poziotinib is supplied as 8-mg and 2-mg tablets and will be administered orally once daily at approximately the same time each morning according to the schedule for each cohort, either for 14 days, followed by 7 treatment-free rest days (**Cohort 1** only) or continuous (**Cohorts 2 and 3** only), during each 21-day cycle. If the morning dose is missed, this dose may be administered any time during the day, at least 8 hours prior to the next scheduled dose.

Loperamide will be supplied by Sponsor and is to be taken by all patients on the following schedule:

- **Days 1 to 56:** 4 mg two times a day (bid), or three times a day (tid) if needed
- **Days 56 until end of treatment:** 4 mg taken as needed, but not to exceed 16 mg/24 hours

The intra-patient dose modification following the first dose administration in **Cohort 2** due to toxicity will be allowed as below:

- After the first occurrence of an AE Grade  $\geq 3$ , the dose of poziotinib will be temporarily withheld. Once the event has recovered to Grade  $\leq 1$ , the treatment can resume at the same dose.
- If the same AE occurs a second time (Grade  $\geq 3$ ), the dose of poziotinib will be reduced.
- No dose reductions below 12 mg/day will be allowed.

No dose modification will be allowed in **Cohort 3** if the toxicity as described above is observed. The patient will be discontinued.

**Reference Therapy, Dose, and Route of Administration:** None

**Efficacy Assessments:**

**Primary Endpoint:**

- The optimal dosing schedule for poziotinib to be used in the clinical development program
- **Objective Response Rate (ORR)**

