## 8.1 Sample Size

Other important treatments for HER2-positive MBC include T-DM1, lapatinib-capecitabine combination, and neratinib. Published ORRs reported for these regimens are 43.6%, 30.8%, and 24%, respectively [22, 24-25]. The purpose of this study is to evaluate the safety and efficacy of poziotinib and identify the optimal dose for future clinical development. No statistical hypothesis testing will be performed.

The enrollment into **Cohort 1** is now complete. A total of 32 patients have received treatment of poziotinib in **Cohort 1**. A total of 30 patients are expected to be enrolled and treated in **Cohort 2**. If the enrollment in **Cohort 2** is stopped due to toxicity, new patients will be enrolled into **Cohort 3**. A total of 20 patients will be enrolled in **Cohort 3**.

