## 8.2 Method of Treatment Assignment

This study is not randomized. Patients will be enrolled sequentially.

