## 8.5 Efficacy Analyses

### 8.5.1 Primary Endpoint

The primary efficacy variables, as described below, will be summarized and analyzed descriptively, along with 95% CI, for each cohort.

- **Objective Response Rate (ORR)** will be assessed according to the Response Evaluation Criteria in Solid Tumors (RECIST) Guidelines, version 1.1 [23] and is defined as the best response [Complete Response (CR) + Partial Response (PR)] recorded from the start of the study until the end of study in patients who received at least 1 dose of poziotinib. The ORR will be based on the EP.

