## 2 OBJECTIVES

### 2.1 Primary Objective

- To establish the dosing schedule for poziotinib to be used in the clinical development program
- To evaluate the Objective Response Rate (ORR) of poziotinib in patients with human epidermal growth factor receptor 2 (HER2)-positive MBC

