### 3.1 Sample Size Considerations

Other important treatments for HER2-positive MBC include T-DM1, lapatinib-capecitabine combination, and neratinib. Published ORRs reported for these regimens are 43.6%, 30.8%, and 24%, respectively [1-3]. The purpose of this study is to evaluate the safety and efficacy of poziotinib and identify the optimal dose for future clinical development.

The original protocol included test of hypotheses with a sample size of 70 as described below. For the primary endpoint of **ORR** in a single-arm study, to test the null hypothesis (hypothesis of no interest in the study) of 24% ( $P_0=0.24$ ) vs. the alternative hypothesis (hypothesis of interest in the study) of 42% ( $P_1=0.42$ ), a sample size of 70 patients achieves 88% power to detect a difference ( $P_1-P_0$ ) of 0.18 using a two sided binomial test. The target significance level is 0.05. The actual significance level achieved by this test is 0.0345. These results assume that the population proportion under the null hypothesis is  $P_0=0.24$ .

In Amendment 1, two lower dose cohorts were added to determine the optimal dose regimen. The test of hypotheses was removed, and the study became a proof-of-concept study. A

sample size of 30 was proposed for **Cohort 2**. If **Cohort 2** was stopped due to toxicity, a sample size of 20 patients was proposed for **Cohort 3**.

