### **5.3 Efficacy Analyses**

All efficacy endpoints will be analyzed based on the Evaluable Population for each cohort.

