### 5.3.2 Primary Efficacy Endpoint

#### Objective Response Rate (ORR)

ORR is the proportion of patients whose BOR is CR or PR. Various ORRs, based on Per Investigator Assessment BOR, Per Sponsor Derivation BOR with confirmation, and Per Sponsor Derivation BOR without confirmation as described in Section 5.3.1, will be estimated using count, percentage and exact (Clopper-Pearson) 95% CI.

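### The dosing-schedule primary endpoint has no variable and no between-cohort estimate, and the response rate beside it leaves out patients who do not complete Cycle 1

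*Protocol*

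**What the plan says.** The protocol synopsis names two primary endpoints. The first is "The optimal dosing schedule for poziotinib to be used in the clinical development program"; the second is ORR. Protocol 2.1 and SAP 2.1 carry the first as a primary objective (SAP: "To establish the dosing schedule for poziotinib to be used in the clinical development program"). Protocol 8.1 and SAP 3.1 add that the study is meant to identify the best dose for later development.

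The analysis text covers ORR only. Protocol 8.5.1 introduces its list with "The primary efficacy variables, as described below, will be summarized and analyzed descriptively, along with 95% CI, for each cohort", and ORR is the sole item. SAP 5.3.2 reads "ORR is the proportion of patients whose BOR is CR or PR", in three versions of best overall response (BOR), each with a Clopper-Pearson interval. SAP 5.3 states "All efficacy endpoints will be analyzed based on the Evaluable Population for each cohort", and SAP 5.4 reports safety by cohort in the Safety Analysis Population (SAF). The Evaluable Population (EP) requires a completed cycle and at least one evaluable post-baseline tumor evaluation (SAP 4).

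On design, protocol 8.2 says "This study is not randomized. Patients will be enrolled sequentially" and protocol 8.1 says "No statistical hypothesis testing will be performed". SAP 3.1 says of Amendment 1 that "The test of hypotheses was removed, and the study became a proof-of-concept study". Protocol 3.1 and SAP 3 give a Safety Data Review rule: Cohort 2 stops if Grade 3 or higher diarrhea, skin rash or stomatitis is seen in at least 3 of 6 or at least 5 of 12 patients. SAP 1 places pharmacokinetics in a separate plan.

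**The concern.** A primary endpoint needs something that can be tabulated. Here the protocol leaves technical detail to the SAP, and the SAP supplies none for the schedule question. Following it exactly produces two sets of per-cohort tables, and a reader has to compare them by eye.

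Two things are at stake. First, a preference between schedules could rest on differences that are within sampling error, because no difference and no interval is reported. Second, the ORR columns being compared come from a set selected after treatment starts. A patient who stops for toxicity before completing Cycle 1 leaves the ORR denominator. If that happens more often on one schedule, that schedule's ORR is raised relative to the other. Early tolerability is what the cohorts were changed to improve (protocol 1.2), so the selection acts on the very feature being compared.

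**Working it through.** **1. The plan's own figure.** SAP 3.1 describes the superseded design: 70 patients, 24% versus 42%, two-sided binomial test, 88% power, achieved level 0.0345. With each exact tail held to 0.025 or less, the test rejects at 25 or more, or at 9 or fewer, responses. The level is 0.0185 + 0.0160 = 0.0345, and power at 42% is 0.883. The figure reproduces, but it tested one pooled rate against 24% and never compared schedules. No figure is given for the current schedule question.

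**2. Are the cohorts a direct schedule contrast?** Planned dose per 21-day cycle is 14 x 24 = 336 mg in Cohort 1 and 21 x 16 = 336 mg in Cohort 2. They differ in schedule and daily dose, not in planned cycle dose.

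**3. Does the safety rule fill the gap?** It governs whether Cohort 2 continues (with a parallel rule for Cohort 3). It is not applied to Cohort 1 and uses no efficacy data. For a true patient-level rate p, taking the second look as cumulative:

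P(stop) = 1 - sum over x = 0, 1, 2 of P(X = x) P(Y <= 4 - x), with X and Y each binomial(6, p).

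| True rate | P(stop Cohort 2) |
|---|---|
| 20% | 13% |
| 33% | 44% |
| 40% | 63% |
| 50% | 84% |

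A cohort with a true rate of 40% continues 37% of the time, so passing the rule says little about how the two schedules compare. SAP 5.4.2.7 tabulates these events by preferred term (with grouped terms for rash and stomatitis). It does not specify the composite Cycle 1 patient rate that the rule uses.

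**4. Precision of a difference.** Inputs: 33 and 34 enrolled (SAP 3). Response counts are illustrative; 24% and 30.8% are published ORRs quoted in protocol 8.1. Toxicity rates are assumptions, shown over a range. Newcombe interval for d = p2 - p1, using Wilson limits (l, u) for each cohort:

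lower = d - sqrt[(p2 - l2)^2 + (u1 - p1)^2]; upper = d + sqrt[(u2 - p2)^2 + (p1 - l1)^2].

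For 8/34 and 8/33, the Wilson limits are 0.1244 to 0.4000 and 0.1283 to 0.4102, and d = -0.007. Lower = -0.007 - sqrt(0.1109^2 + 0.1678^2) = -0.208. Upper = -0.007 + sqrt(0.1647^2 + 0.1141^2) = +0.193.

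| Cohort 2 vs Cohort 1 | Difference (points) | 95% CI |
|---|---|---|
| ORR 8/34 vs 8/33 | -1 | -21 to +19 |
| ORR 10/34 vs 10/33 | -1 | -22 to +20 |
| ORR 14/34 vs 8/33 | +17 | -5 to +37 |
| Toxicity 7/34 vs 7/33 | -1 | -20 to +19 |
| Toxicity 11/34 vs 11/33 | -1 | -23 to +21 |
| Toxicity 17/34 vs 16/33 | +2 | -21 to +24 |

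Protocol 8.1 gives 32 treated in Cohort 1. Using 8/34 versus 8/32 moves the first row only to -1 (-22 to +19).

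**5. Detectability.** With a normal approximation, 33 versus 34 patients and 24% in one cohort, power for a true 20-point difference is about 41% (pooled variance) or 42% (unpooled). Power reaches 80% at roughly 32 to 33 points. For 24% versus 42% it is about 34%, and 80% power would need 106 per cohort.

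**6. Effect of the EP.** The number excluded is not stated. Assume 8 responders among 33 treated and 1, 3 or 5 excluded non-responders. ORR then reads 8/32 = 25.0%, 8/30 = 26.7% or 8/28 = 28.6%, against 8/33 = 24.2%. An imbalance of that kind alone could shift the comparison by up to about 4 points.

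**The case against.** The strongest defence is that the study is openly descriptive. Tests were removed, the study is called proof-of-concept, and ORR, disease control, progression, adverse events, dose intensity and reductions all appear by cohort. The sponsor can weigh these side by side. That stands, so a reader who infers that the plan cannot answer the schedule question goes too far. What is missing is a prespecified contrast or criterion.

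Second, the design moves on tolerability: the SAP's summary of changes says the original dose was not well tolerated, and the safety rule governed Cohort 2. This is the nearest thing to a criterion and deserves credit, but neither document ties it to the endpoint.

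Third, the separate pharmacokinetic plan was not available for review and may bear on schedule. The SAP does not link it to this endpoint.

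Fourth, a difference with an interval does not itself define which schedule is best, and the contrast is confounded. Cohort 1 enrolled under the original protocol and Cohort 2 under Amendments 1 and 2. Amendment 2 removed the cap on prior HER2 regimens, lowered the neutrophil threshold, shortened the washout and added a life-expectancy criterion. Both points stand. They argue for estimation with a caution, not for leaving the difference unreported.

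Two further inferences are unsupported. The absence of a formal test is not a fault: the documents deliberately have none, and power would be low. Nor does an interval half-width near 20 points mean that 20-point differences are reliably distinguished (working, step 5).

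**Conclusion.** The point holds in this form: the first primary endpoint has no operational variable and no between-cohort estimate, and the only ORR set planned can distort a comparison of schedules with different early tolerability. It does not show that the schedule choice would be wrong or that no judgement could be made.

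On size, intervals for a difference run about 20 points either side of zero when the cohorts are alike, and an observed 17-point gap in ORR would still include zero. These figures assume illustrative counts and that all 33 and 34 enrolled patients contribute. The size and direction of any EP distortion are unknown, because the documents do not give exclusions by cohort. The change should be made: a primary endpoint is affected and the remedy is small.

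**What to change.** Add one SAP subsection and one table for this objective, giving descriptive Cohort 2 minus Cohort 1 differences in the SAF:

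- ORR, using one named BOR version, with non-evaluable patients counted as non-responders; Newcombe 95% CI. The EP result can stay beside it.
- Patients with any Grade 3 or higher diarrhea, rash or stomatitis in Cycle 1; Newcombe 95% CI.
- Patients discontinuing for adverse events; Newcombe 95% CI.
- Relative dose intensity, as a difference in means or medians with its own 95% CI, since it is continuous and Newcombe intervals do not apply. SAP 5.4.1 describes 28-day cycles in words but divides by 21 in the formula; these must be reconciled first.

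State that no test is done and that the contrast is sequential, unrandomised and confounded by the Amendment 2 eligibility changes. Refer to the pharmacokinetic plan if it informs the choice. If outcome data have already been reviewed by cohort, label the table as added afterwards. At the least, list the item as an objective only, not as an endpoint.

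The cost is one table from data already collected, and an ORR that may be slightly lower than in the EP. The choice of schedule stays with the sponsor.
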